## 6. Abstract

*Background:* Myocardial infarction with non-obstructive coronary arteries (MINOCA) represents about 6-8% of patients presenting with myocardial infarction. Initially believed to be a benign condition, is now becoming clear that MINOCA is associated with a significant risk of mortality, rehospitalization, disability and angina burden, with high socioeconomic costs. However, to date there are no prospective clinical trials in this population and treatment of these patients is not still defined, also because there are multiple pathogenic mechanisms underlying MINOCA.

*Objectives:* The aim of our study is to evaluate if the use of a precision-medicine approach with a specific therapy tailored on the underlying pathogenic mechanism will improve the quality-of-life in MINOCA patients (*primary objective*). We further aim at investigating wherever a precision-medicine approach will improve the prognosis, healthcare related costs, and if that a different profile of plasma biomarkers and microRNAs may serve as diagnostic tools for detecting specific causes of MINOCA and to assess response to therapy (*secondary objectives*). Finally, beyond its pivotal role in differential diagnosis, we hypothesize that cardiac magnetic resonance (CMR) may provide a morphological and functional cardiac characterization as well as help in the prognostic stratification (*secondary objective*).

*Methods:* We will include 180 patients aged >18 years hospitalized for MINOCA randomized 1:1 to a "precision medicine approach" consisting of a comprehensive diagnostic work-up, analysis of circulating biomarkers and micro RNA expression profile and pharmacological treatment specific for the underlying cause *versus* a "standard approach" consisting of routine diagnostic work-up and standard medical treatment.

## INTRODUCTION

**6.a** Randomized multicenter prospective superiority phase IV trial comparing “precision medicine approach” *versus* “standard of care” in improving the prognosis and/or the quality-of-life of patients presenting with MINOCA. Patients will be randomized 1:1 to “precision medicine approach” consisting of a comprehensive diagnostic work up aim at elucidating the pathophysiological mechanism of MINOCA and consequently a tailored pharmacological approach *versus* “standard of care” consisting of standard diagnostic algorithm and therapy for myocardial infarction.

**6.b Background:** Myocardial infarction with non-obstructive coronary arteries (MINOCA) represents about 6-8% of all patients presenting with acute myocardial infarction (MI) referred for coronary angiography. MINOCA is defined by the evidence of MI with normal or near normal coronary arteries on angiography, in absence of a specific alternate diagnosis for the clinical presentation (i.e. sepsis, myocarditis, pulmonary embolism). Notably, there is a variety of causes underlying MINOCA including coronary plaque rupture/erosion, epicardial or microvascular spasm, and coronary embolism. Therefore, MINOCA should not be considered as a single entity but a heterogeneous working diagnosis that requires a comprehensive evaluation to elucidate the potential underlying cause. Several studies have shown that MINOCA patients have 1-year mortality and rehospitalization rate similar to those patients with acute MI with obstructive coronary artery disease (MICAD). Furthermore, approximately 25% of patients with MINOCA will experience angina in the subsequent 12 months, at least as high as reported in patients with MICAD, with a significant impact on quality of life and healthcare related costs. Angina symptoms have also relevant socioeconomic consequences because patients with angina without evidence of CAD have the same increased probability of future disability pension and premature exit from the workforce as patients with obstructive CAD. This is of crucial importance, because MINOCA patients are usually younger than patients with MICAD. A comprehensive evaluation and a multimodality assessment aiming at uncovering the aetiology should be pursued, in order to implement tailored therapeutic approaches targeted to the specific underlying cause. Indeed, the management of MICAD has well-established evidence-based guidelines, while the management of MINOCA has a limited evidence-based literature, with no prospective randomized controlled trials undertaken to date. In particular, a precision medicine approach is important in MINOCA patients because of the multiple causes underlying this condition. Importantly, a precision-medicine approach had already proved its efficacy

in patients with stable angina and non-obstructive CAD. Indeed, the landmark Coronary Microvascular Angina (CorMicA) trial showed that in these patients a strategy of adjunctive invasive testing for disorders of coronary function linked with stratified medical therapy led to improvement in patient outcomes, including reduction in angina severity and better quality of life. If a similar precision-medicine approach is effective also in patients with MINOCA has never been assessed. We previously demonstrated that patients with a positive provocative test for epicardial or microvascular spasm had a higher occurrence of future cardiac events, thus identifying high-risk MINOCA patients that may need a more aggressive therapy. Moreover, biochemical profile of MINOCA patients is still largely unknown and whatever exist a unique profile associated with specific pathophysiological mechanisms remains unknown. Endothelin-1 (ET-1) and neuropeptide Y (NPY) are endogenous vasoactive substances regulating coronary vasomotion involved in coronary spasm. On the other hand, elevated plasma levels of soluble CD40L and C-reactive protein (CRP) are involved in inflammatory activation during MI with plaque rupture. Moreover, also circulating miRNA may be associated with specific pathophysiological mechanisms of MINOCA, and may represent new promising diagnostic tools. Particularly, the up-regulation of miR-16 and miR-26a and the down-regulation of miR-1 and miR-133, have been reported to characterize coronary microvascular spasm, whereas, miR-145 and miR-222 may help in identifying patients with epicardial spasm. Finally, miR-155-5p, miR-483-5p and miR-451a have been suggested as novel biomarkers for the early identification of plaque rupture. However, miRNA assessment in MINOCA patients has never been performed. In the absence of dedicated randomized controlled trials, current guidelines do not specifically address the issue about acute and long-term management of patients with MINOCA. The effects of secondary preventive treatments proven beneficial in patients with MICAD are unknown in MINOCA patients. The "one-size-fits-all" approach used for MICAD treatment may not apply uniformly to all MINOCA patients, which instead should be "personalized" depending on the underlying pathophysiological mechanism responsible for the clinical presentation. Thus, the next key step in the management of MINOCA is to demonstrate the benefits of tailored therapies on cardiovascular and quality-of-life outcomes. With this prospectively designed trial, we have the opportunity to test the prognostic value of a targeted therapeutic approach based on the identification of the underlying cause. Of importance, the results deriving from our trial may open the way for a new pathophysiology-driven approach with cause-target therapies personalized for the mechanisms of MINOCA.

**6.c** There is a limited agreement regarding the acute and long-term medical management of patients with MINOCA. The results of a large observational study of MINOCA patients from the

SWEDHEART registry have shown a significantly lower rate of cardiovascular events associated with the use of statins and ACEi/ARB, a trend for a lower event rate with the use of  $\beta$ -blockers, while dual antiplatelet therapy (DAPT), a cornerstone of therapy for MICAD patients, failed to improve prognosis. An important limitation of this study is the heterogeneous nature of MINOCA cohort, without discerning the mechanism leading to myocardial infarction. Given these therapeutic shortcomings in this evolving area of clinical research, multicentre randomized clinical trials are needed to determine the optimal medical therapy for MINOCA based on the specific cause of the syndrome. Importantly, a precision-medicine approach had already proved its effectiveness in patients with stable angina and/or signs of ischemia but no obstructive coronary artery disease (INOCA). Indeed, the CorMicA trial showed that in patients with INOCA a strategy of adjunctive invasive testing for disorders of coronary function linked with stratified medical therapy led to improvements in patient outcomes, including reduction in angina severity and better quality of life. Similarly, the identification of functional alterations of coronary circulation is relevant in the clinical setting of MINOCA. We previously demonstrated that MINOCA patients with a positive test result (epicardial or microvascular spasm) had a significantly higher occurrence of cardiovascular events, thus identifying a high-risk subset of patients that may need a more aggressive therapy and a closer follow-up.

Moreover, information about cardiac structure and function as well as plasma biochemical profile associated with the different causes of MINOCA is scanty. Beyond its role in differential diagnosis, CMR may help in the morphological and functional cardiac characterization as well as in the prognostic stratification. Biochemical profile of patients with MINOCA is still unidentified and whatever exist a unique profile associated with specific pathophysiological mechanisms remains unknown. Endothelin-1 (ET-1) and neuropeptide Y (NPY) are endogenous vasoactive substances regulating coronary vasomotion, with higher circulating levels in patients with coronary microvascular and epicardial spasm. Elevated plasma levels of soluble CD40L and CRP, two inflammatory biomarkers associated with inflammation and thrombus formation, have been described in patients with MI due to acute plaque destabilization. Recent findings have shown that levels of specific circulating miRNA may have a close association with specific pathophysiological mechanisms of myocardial infarction (i.e. plaque rupture, microvascular spasm or epicardial spasm). Particularly, a unique signature, comprising the up- regulation of miR-16 and miR-26a and the down-regulation of miR-1 and miR-133, has been reported to characterize coronary microvascular spasm, whereas miR-145 and miR-222 may help to identify patients with epicardial spasm. Finally, a recent study identified miR-155-5p, miR-483-5p and miR-451a, as novel biomarkers for the early

identification of plaque rupture. However, the role of circulating plasma biomarkers and miRNA in MINOCA patients has never been investigated.

## 7. Study objectives:

Primary objectives:

- To test if a precision-medicine approach with a careful investigation of the MINOCA aetiology and consequent aetiology-based treatment may result in improved quality of life outcomes.

Secondary objectives:

- To evaluate if the use of a precision-medicine approach with a specific therapy tailored on the MINOCA pathogenic mechanism will improve the prognosis.
- To assess if a precision-medicine approach with a careful investigation of the MINOCA aetiology and consequent aetiology-based treatment may result in reducing healthcare related costs.
- To test wherever a plasma circulating biomarker profile may be able to differentiate between the different causes of MINOCA, helping to identify the underlying pathophysiological mechanisms and to stratify prognosis and response to medical therapy.
- To test wherever cardiac magnetic resonance (CMR) may provide a morphological and functional cardiac characterization as well as help in the prognostic stratification in MINOCA.

**8. Study design:** Randomized multicenter prospective superiority phase IV trial comparing “precision medicine approach” *versus* “standard of care” in improving the prognosis and/or the quality-of-life of patients presenting with MINOCA. Patients will be randomized 1:1 to “precision medicine approach” vs “standard approach”.

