## **12. Outcomes of interests:**

Primary endpoints:

- Angina status and quality of life (evaluated using the Seattle Angina Questionnaire [SAQ]) at 1-year follow-up in patients with MINOCA.

[figure not shown]
\* To reduce the risk of detection and performance bias, a team of 2 cardiologists blinded to group allocation and belonging to an external cardiology unit will submit and collate the questionnaires from study participants.

Secondary endpoints:

- Rates of major adverse cardiovascular events (MACE; composite of all-cause mortality; re-hospitalization for myocardial infarction, stroke or heart failure; repeated coronary angiography) at 1-year follow-up in MINOCA patients.
- Healthcare primary and secondary related-costs (including costs for tests, procedures and outpatient visits or medicines) and socioeconomic burden of MINOCA patients.
- Ability of different circulating biomarkers (ET-1, NPY, CRP, sCD40L and miRNA [miR-16, miR-26a, miR-145, miR-222, miR-155-5p, miR-483-5p and miR-451]) as diagnostic biomarker and stratification tool for specific causes of MINOCA.
- Ability of CMR in evaluating different mechanisms of MINOCA and their prognostic value.

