## Study timeline

# Study Timeline

### *T 0 (index hospitalization for MINOCA):*

During the index hospitalization the study investigators, after a careful evaluation of the inclusion and exclusion criteria of the patients, will collect:

- Anagraphic data
- Personal information: weight, height, BMI
- Vital parameters (blood pressure, heart rate, oxygen saturation)
- Therapy at admission and at discharge (concomitant medications included)
- Cardiovascular risk factors: family history of early coronary artery disease (first degree relative with a history of myocardial infarction <60 years), diabetes mellitus [fasting blood glucose >126 mg/dL or treated diabetes mellitus (intake of a diabetic diet or oral hypoglycaemic agents), according to the American Diabetes Association (ADA) criteria], hypercholesterolemia (total cholesterol >200 mg/dL or treated hypercholesterolemia), smoking (current), and hypertension (systolic blood pressure >140 mmHg and/or diastolic blood pressure >90 mmHg or treated hypertension).

- Relevant comorbidities: anaemia, chronic kidney disease, atrial fibrillation, history of stroke/TIA, peripheral vascular disease
- ECG features (ST segment elevation/depression or T wave inversions, atrioventricular blocks, arrhythmias)
- Trans-thoracic color-Doppler echocardiography (chamber volumes, systolic and diastolic function)
- Data on coronary angiography and ventriculography (presence/absence of non-obstructive CAD, micro vs epicardial coronary spasm, “hazy” angiographic images, TIMI flow, LVEDP)
- Laboratory data (creatinine, full blood count, Troponin I peak, CK-MB peak, NT-proBNP, CRP)

For patients randomized to “*precision medicine approach*”:

- OCT (if coronary plaque rupture/erosion is suspected) at the time of coronary angiography in the cath-lab.
- Acetylcholine provocative test (to assess the presence of coronary vasospasm) at the time of coronary angiography in the cath-lab.
- TE-Echo and/or CE-Echo (if distal/microvascular embolization is suspected) during the hospitalization at the echo laboratory
- CMR with contrast media: anatomical and morphological data
- Blood sampling for circulating biomarkers and miRNA expression profile at the time or within the 12 hours from coronary angiography. Blood sampling will be processed and analysed in the research laboratory of the Department of Cardiovascular Science. Biological aliquots will be preserved at XBiogem Biobank at Fondazione Policlinico Universitario A. Gemelli IRCCS, Rome.

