### *Definition of the MACE*

MACE analysis includes:

- All cause death:
  - Cardiac death (in which a direct cause attributable to cardiac disease is present);
  - Sudden cardiac death (in which cardiac death occurred out of the hospital and suddenly; or in the hospital due to ventricular arrhythmias unrelated to other concomitant cardiac conditions);
  - Non-cardiac death (in which the event of death is considered not to be a direct consequence of cardiac disease);
- Hospitalization in which the main diagnosis is myocardial infarction, stroke or heart failure;
- Repeated coronary angiography.

The analysis will consider time to first event and time to each event.

Safety parameters will include data deriving from history and physical examination performed at each visit, laboratory data and results of functional and imaging tests. To enhance detection of adverse events between visits, all patients will be encouraged to contact the research team at any time with concerns or any perceived changes in their healthcare status.

**14. Sample size calculation:** Sample size calculation for the primary endpoint: to detect a mean group difference of change in SAQ score of 9 U, we calculated that a sample size of 70 patients per group (140 patients total) gave 80% power to detect a between-group difference in SAQ. This

calculation assumed a 2-tailed 5% significance level. This projected calculation assumed an SD of 19 U and was consistent with previous studies (see landmark CorMicA trial). However, we extended the sample size at 180 patients to avoid any reduction of statistical power due to patients lost at follow-up or due to poor compliance to medical therapy.

**15. Timeline:** At 36 months all patients will be enrolled and will have completed the follow-up. The study will be considered ended after the date of last patient last visit (LPLV). Blood samples will be analysed for assessment of circulating biomarkers and miRNA to detect associations with specific mechanisms underlying MINOCA, for stratification of prognosis and to evaluate response to medical therapy. Furthermore, CMR sequences will be analysed to detect functional and structural characteristics associated with specific mechanisms underlying MINOCA and with for stratification of prognosis.

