### **33. Management of biological materials**

**Blood sample collection:** 42 mL venous blood samples will be collected at the time of coronary angiography or within 12 hours from coronary angiography. Biochemical profile for evaluating the expression of Endothelin-1 (ET-1) and Neuropeptide Y (NPY), C-Reactive Protein (CRP), soluble CD40 ligand (sCD40L) will be performed on plasma and serum samples at baseline with ELISA kit.

Peripheral blood mononuclear cells (PBMC) will be isolated from EDTA blood by density gradient centrifugation. Serum and PBMC expression levels for deregulated miRNAs will be performed on the same samples to test circulating levels of miR-16, miR-26a, miR-145, miR-222, miR-155-5p, miR-483-5p and miR-451a with Serum microRNA microarray commercial kit. Coded plasma, serum and PBMC samples will be stored at -80°C at FPG XBiogem Biobanc.

All experiments and analysis will be performed at the “Cellular and molecular cardiology laboratory” of the Department of Cardiovascular Science. Coded plasma, serum and PBMC sample from patients enrolled in the other centers (Centro Cardiologico Monzino IRCCS and IRCCS Policlinico San

Donato) will be collected with the same protocol for procedure standardization and will be shipped to our Unit.

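### Biomarkers are meant to inform response to therapy, but the panel is drawn once and listed for the precision arm only, so for 10 of 11 markers response cannot be separated from prognosis

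*Combined protocol and SAP*

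**What the plan says.** Three places in the protocol tie the biomarkers to treatment response, with different verbs.

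- Section 6 (Abstract): the profile "may serve as diagnostic tools for detecting specific causes of MINOCA and to assess response to therapy".
- Section 7 (Study objectives): "helping to identify the underlying pathophysiological mechanisms and to stratify prognosis and response to medical therapy".
- Section 15 (Timeline): samples will be analysed "for stratification of prognosis and to evaluate response to medical therapy".

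The biomarker endpoint in Section 12 is narrower. It covers the markers "as diagnostic biomarker and stratification tool for specific causes of MINOCA" and does not mention response.

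On collection, Section 33 gives one window: "42 mL venous blood samples will be collected at the time of coronary angiography or within 12 hours from coronary angiography". It adds that the protein assays "will be performed on plasma and serum samples at baseline with ELISA kit". The T0 list in the study timeline has the item "Blood sampling for circulating biomarkers and miRNA expression profile at the time or within the 12 hours from coronary angiography" under the precision-arm heading. Section 11a and the assessment schedule also place it there, and the standard-arm lists omit it. The contacts at 3, 6 and 9 months are telephone interviews, and the 12-month visit lists no blood draw. Section 11a starts drug treatment after angiography, during the index admission. CRP appears a second time, in the routine T0 laboratory data, which are not restricted to one arm. Section 20 gives no biomarker analysis.

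**The concern.** Response to therapy has two usual meanings in a biomarker objective. One is that the marker changes under treatment, which needs at least two samples per patient. The other is that the baseline marker identifies who gains from the tailored strategy over standard care, which needs the marker in both arms. As listed, the sampling plan provides neither for most of the panel.

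What is left is the association of a baseline marker with outcome among precision-arm patients. Drugs in that arm are chosen by cause, and the markers were selected because they are thought to track cause, so marker, cause and drug class will tend to move together. If such an association were labelled response, a prognostic finding would be presented as a predictive one.

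**Working it through.** **1. Markers affected.** Section 12 names ET-1, NPY, CRP and sCD40L (4) and seven miRNAs, 11 in all. CRP is also routine laboratory data in both arms, which leaves 11 − 1 = 10 listed for the precision arm only.

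**2. Change on therapy.** One draw per patient is scheduled, so a within-patient change is undefined for all 11 markers; CRP has no follow-up measurement either. The single sample is not a guaranteed pre-treatment value: it may be taken up to 12 hours after angiography, and drugs start after angiography.

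**3. Marker-by-treatment interaction.** Let A be arm (1 = precision) and M the marker:

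E(Y) = b0 + b1·A + b2·M + b3·A·M.

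If M is seen only where A = 1, this becomes (b0 + b1) + (b2 + b3)·M. The design matrix has rank 2 for four parameters; with M seen in both arms it has rank 4. Standard-arm outcomes without M add only an arm mean, b0 + b2·E(M), which does not separate b2 (prognosis) from b3 (differential benefit). More patients do not help.

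**4. The plan's own sample size.** Section 14: difference 9, SD 19, two-sided 5%, 80% power.

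n per arm = 2 × (1.960 + 0.842)² × (19/9)² ≈ 70, as stated. It concerns the SAQ comparison; no figure is given for the biomarker objective.

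**5. A marker available in both arms (CRP as planned, or the panel if sampling were extended).** Assumptions, not in the plan: the SD of 19, which Section 14 gives for change, also applies to 12-month SAQ; the marker is binary with prevalence p equal in the two arms. With m patients per arm:

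SE = 19 × √[2/(m·p) + 2/(m·(1 − p))]; minimum detectable interaction = 2.802 × SE.

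For m = 90 and p = 0.5, SE = 19 × √(2/45 + 2/45) = 5.66, giving 15.9 units.

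| Total N | p | Minimum detectable interaction (units) | Power for 9 units |
|---|---|---|---|
| 180 | 0.5 | 15.9 | 35.5% |
| 180 | 0.3 | 17.3 | 30.7% |
| 180 | 0.2 | 19.8 | 24.5% |
| 140 | 0.5 | 18.0 | 28.8% |
| 140 | 0.3 | 19.6 | 25.0% |
| 140 | 0.2 | 22.5 | 20.1% |

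**6. What the precision arm alone can show.** The smallest correlation between baseline marker and 12-month outcome detectable with 80% power is tanh[2.802/√(n − 3)]: 0.29 for n = 90 (180/2) and 0.33 for n = 70 (140/2).

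**The case against.** The best defence rests on the verb in Section 7. To stratify response is a baseline aim and needs no repeat sample: a baseline level can be related to 12-month SAQ or MACE. Within one cause, marker level can also vary while the class of drug stays roughly fixed, so confounding by cause is not complete. This stands as far as it goes, since the association is estimable. But without a comparator it cannot be told apart from prognosis, which Section 7 already names separately. Nor does this reading fit the abstract and Section 15, which speak of assessing and evaluating response. Within-patient improvement in SAQ cannot fill the gap, because the schedule lists SAQ at 12 months only.

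Section 33 names no arm and could be read as allowing sampling of everyone. Every arm-specific list, however, puts the draw in the precision arm alone. If both arms were intended, those lists must be corrected, and the power figures above would then apply to the whole panel.

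The defence is also right that Section 12 omits response and that Section 20 plans no such analysis. This makes the problem a mismatch between objective, endpoint and sampling. A reader might infer that the trial will report unsupported response findings; the documents do not show that.

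**Conclusion.** The point holds. For ET-1, NPY, sCD40L and the seven miRNAs (10 of 11 markers), the planned sampling supports neither change on therapy nor a marker-by-treatment interaction. This rests on reading the arm-specific lists as complete.

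Three stronger readings are not supported.

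- A reader might infer that blood is drawn before treatment and that no sample follows it. The 12-hour window can extend past the start of drugs, so all that can be said is that no follow-up sample is scheduled.
- A reader might infer that no standard-arm patient contributes any marker. CRP is routine T0 data in both arms, so a baseline CRP-by-arm interaction can be fitted, with roughly 20–36% power for 9 units across the totals and prevalences assumed above.
- A reader might infer that the biomarker work is uninformative. Discrimination of cause and prognostic association within the precision arm remain estimable.

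Severity is minor to moderate: an aim stated three times that the design cannot deliver, but a secondary one that leaves the primary comparison untouched.

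**What to change.** Remove the response-to-therapy wording for the biomarkers from Sections 6, 7 and 15. Limit the objective to (a) discrimination between causes and (b) prognostic association of baseline markers with 12-month outcome, both within the precision arm, and state that no treatment-response claim will be made. This agrees with Section 12, which already omits response. If (b) is kept, Section 12 should name it and Section 20 should give its method.

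The cost is one narrowed secondary objective and possibly a protocol amendment under Section 25. No extra patients, samples or visits are needed.

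The alternative is to keep the aim and supply the data: the panel in both arms, a follow-up sample (the 12-month clinic visit already exists) and a specified analysis. That adds samples and assays. At 180 patients it would still leave only about 25–36% power for a 9-unit interaction, so narrowing the objective is the proportionate choice.
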